7. ADVERSE REACTIONS

The potential adverse reactions of generic Clindamycin Phosphate and Benzoyl Peroxide Topical Gel 1.2%/3.75% are anticipated to be similar to those observed in Onexton™ Topical Gel (Clindamycin Phosphate and Benzoyl Peroxide Topical Gel 1.2%/3.75%). Adverse reactions related to treatment with Onexton™ Topical Gel include cutaneous irritation (erythema, scaling, itching, stinging and burning).

The following adverse reactions occurred in less than 0.5% of patients treated with Onexton™ topical gel: contact dermatitis (0.4%), application site burning sensation (0.4%), application site pruritus (0.4%) and rash (0.4%). Most local skin reactions either were the same as baseline or increased and peaked around week 4 and were near or improved from baseline levels by week 12.

Protocol No: PRG-NY-15-003

Systemic absorption of clindamycin has been demonstrated following topical use of clindamycin. Diarrhea, bloody diarrhea, and colitis (including pseudomembranous colitis) have been reported with the use of topical and systemic clindamycin. When significant diarrhea occurs, study medication should be discontinued. Severe colitis has occurred following oral and parenteral administration of clindamycin with an onset of up to several weeks following cessation of therapy. Studies indicate a toxin(s) produced by clostridia is one primary cause of antibiotic-associated colitis. The colitis is usually characterized by severe persistent diarrhea and severe abdominal cramps and may be associated with the passage of blood and mucus. Endoscopic examination may reveal pseudomembranous colitis. Stool culture for *Clostridium difficile* and stool assay for *Clostridium difficile* toxin may be helpful diagnostically.

Anaphylaxis, as well as allergic reactions leading to hospitalizations, has been reported in post-marketing use of products containing clindamycin/benzoyl peroxide.

7.1 Departure from the Protocol for Individual Subjects

When an emergency occurs requiring a departure from the protocol for a subject, departure will be only for that subject. In such circumstances, the investigator or other physician in attendance will contact the Medical Monitor or Perrigo by telephone and follow up with a written description as soon as possible. The overseeing IRB should also be notified.

7.2 Definitions

An adverse event (AE) is defined as any untoward medical occurrence in a subject administered a medicinal product and which does not necessarily have to have a causal relationship with this treatment. An adverse event can therefore be any unfavorable and unintended sign (for example, an abnormal laboratory finding), symptom, or disease temporally associated with the use of a medicinal product, whether or not considered related to this medicinal product.

A serious adverse event (SAE) is an adverse event that results in any of the following outcomes:

- death
- life-threatening event (i.e., the subject was, in the opinion of the investigator, at immediate risk of death from the event as it occurred. It does not include an event that, had it occurred in a more severe form, might have caused death)
- requires in-subject hospitalization or prolongs hospitalization
- a persistent or significant disability/incapacity or substantial disruption of the ability to conduct normal life functions
- congenital anomaly/birth defect
- Other adverse events that may be considered serious based upon appropriate medical judgment, may jeopardize the subject and may require medical or surgical intervention to prevent one of the outcomes listed above.,

Immediately Reportable Adverse Events (IRAE): Any serious AE or any AE that necessitates discontinuation of study medication, including pregnancy.

Protocol No: PRG-NY-15-003

Unexpected Adverse Event: An unexpected event is any adverse drug experience, the specificity or severity of which is not consistent with the current approved product labeling (package insert) for the study medication, the Investigator's Brochure, or as described in the clinical protocol and consent materials.

Intensity of Adverse Events: The maximum intensity of an AE during a day should be recorded on the CRF. If the intensity of an AE changes over a number of days, then separate entries should be made having distinct onset dates for the changes in severity.

Mild - AEs are usually transient, requiring no special treatment, and do not interfere with subject's daily activities.

Moderate - AEs typically introduce a low level of inconvenience or concern to the subject and may interfere with daily activities, but are usually ameliorated by simple therapeutic measures.

Severe - AEs interrupt a subject's usual daily activity and traditionally require systemic drug therapy or other treatment.

Causal Relationship to Study Medication: The following criteria should be used in assessing the apparent causal relationship of an AE to study medication.

Definitely - The AE:

- follows a reasonable temporal sequence from study medication administration
- abates upon discontinuation of the study medication (dechallenge)
- is confirmed by reappearance of the reaction on repeat exposure

Probably - The AE:

- follows a reasonable temporal sequence from study medication administration
- abates upon discontinuation of the study medication (dechallenge).
- cannot be reasonably explained by the known characteristics of the subject's state.

Possible - The AE:

- follows a reasonable temporal sequence from study medication administration
- but that could readily be produced by a number of other factors.

Unlikely - The AE:

- follows a reasonable temporal sequence from study medication administration.
- could have been produced by either the subject's clinical state or by study medication administration.

Not related - The AE:

- does not have a reasonable temporal association with the administration of study medication
- has some other obvious explanation for the event.

7.3 Eliciting and Reporting of Adverse Events

The investigator will periodically assess subjects for the occurrence of adverse events. [REDACTED]

[REDACTED] All adverse events (as defined in Section 7.2), either observed by the Investigator or one of his/her medical collaborators, or reported by the participant spontaneously, or in response to direct questioning, will be reported and documented in the source and the study reporting forms. When reporting an adverse event, the Investigator must assign a severity grade to each event and declare an opinion on the relatedness of the event to the study medication or procedure. Serious or unexpected adverse events must be reported to Perrigo **within 24 hours** of when the Investigator first learns of the occurrence of the event.

Adverse events will be documented in the source document and recorded in a timely manner on case report forms. Adverse events (e.g., worsening of acne*) that are identified at the last assessment visit (or the early termination visit) must be recorded on the AE case report form (CRF) with the status of the AE noted.

* Worsening of the subject's acne may be expected from application of the study medication. This will only be reported as an adverse event if a subject is discontinued from the study or an alternate treatment is required.

Adverse event reporting begins from the signing of informed consent/assent. Adverse events should be followed until resolved or 30 days after the final study treatment. In any case, serious adverse events that are not resolved or considered to be chronic within 30 days of the final study treatment must be followed by the investigator until they become resolved or are considered to be chronic (stabilized for at least 30 days). All events that are ongoing at this time will be recorded as ongoing on the CRF.

7.3.1 Expedited Reporting Responsibilities of the Study Center

For any serious or unexpected adverse event, the sponsor must be notified **within 24 hours** of when the Investigator first learns of the occurrence of the event. Expedited reporting requirements for serious adverse events are described below. Adequate information must be collected with supporting documentation to complete a standard report for submission to Perrigo. The adverse event term on the AE case report form (CRF) and the SAE report should agree exactly. Special attention should be given to recording hospitalizations and concomitant medications.

Subjects with unresolved adverse event(s) or serious adverse event(s) should be followed by the investigator until the events are resolved, events determined to be chronic or the subject is lost to follow-up. Resolution means the subject has returned to the baseline state of health, or the investigator does not expect any further improvement or worsening of the adverse event. The investigator should continue to report any significant follow-up information to the sponsor up to the point that the event has resolved. Any serious adverse event reported by the subject to the investigator that occurs within 30 days after the last assessment, and are determined by the

investigator to be reasonably associated with the use of the study medication, should be reported to the sponsor within 24 hours of when the Investigator first learns of the occurrence of the event.

When reporting a serious adverse event (SAE) the Investigator (or the Study Coordinator) will promptly report any serious adverse event or pregnancy by telephone to [REDACTED] [REDACTED] immediately after the investigator becomes aware of the event. An SAE form should be completed and sent by fax, email, or overnight courier to [REDACTED] within 24 hours of knowledge of the event by the site. In many cases, only preliminary information will be available. Appropriate follow up information should be sought (hospital discharge summaries, operative reports etc.) and a follow up SAE report form submitted. A designation of causality from the study medication should always be included with a follow up report. Assess and report the causality of the event.

7.3.2 Submitting an Expedited Safety Report to the IRB

Once [REDACTED] receives all supporting documentation for the reported event, the Medical Monitor, in conjunction with Perrigo, will determine if the safety report is eligible for expedited review.

[REDACTED] will log the initial event and will notify the sponsor that an event has been reported within 1 business day after initial receipt. [REDACTED] will complete the review of the event, enter information into their safety database and generate the report. This form, as well as other supporting documentation, will be forwarded to [REDACTED] Medical Monitor for review. [REDACTED] will finalize the report and distribute it to the sponsor within 2 days after initial receipt. When expedited safety reporting to regulatory authorities is indeed required, the Investigator should review and update any newly available materials at once. Follow-up queries may be sent to the study center to further clarify the event.

Each expedited safety report will routinely include a brief cover memorandum, the completed report, and any additional pertinent information recommended by [REDACTED], Perrigo, or study Medical Monitor. Once the report is assembled, the Principal Investigator must submit the expedited safety report to the IRB within the required reporting timeframe. Follow-up reports should be submitted when requested or when pertinent information becomes available.

When a Principal Investigator receives an expedited safety report from [REDACTED] or the sponsor detailing adverse events occurring at other study centers under this protocol, it must be promptly submitted to the study center's IRB. The Principal Investigator must retain a copy of such reports as submitted to their IRB in the site's study Regulatory Binder.

7.4 SAE & AEs Requiring Discontinuation of Study Drug, including Pregnancies

ANY SAE, WHICH OCCURS AFTER A SUBJECT HAS ENTERED THE STUDY, WHETHER OR NOT RELATED TO STUDY MEDICATION, MUST BE REPORTED TO [REDACTED] AND PERRIGO IMMEDIATELY (WITHIN 24 HOURS) VIA TELEPHONE OR FACSIMILE. IF INITIALLY REPORTED VIA TELEPHONE, THIS MUST BE FOLLOWED-UP BY A FACSIMILE OF THE WRITTEN SAE REPORT WITHIN 24 HOURS OF THE CALL TO [REDACTED].

Non-serious events that require discontinuation of study medication (including laboratory abnormalities) should be reported to Perrigo immediately and within 1 working day.

Protocol No: PRG-NY-15-003

Subjects who discontinue due to experiencing adverse events should be followed clinically until their health has returned to baseline status, or until all parameters have returned to normal. It is expected that the investigator will provide or arrange appropriate supportive care for the subject.

A subject who experiences a severe adverse event related to study drug will be discontinued from the study.

The notification about any serious adverse event should be directed to:

7.4.1 Pregnancy

At the time a Principal Investigator or site personnel becomes aware that a study participant became pregnant following study participation, the Principal Investigator or designee will report the pregnancy immediately by phone and/or by faxing a completed Pregnancy Report to [REDACTED] within one working day of being notified of the pregnancy report.

The report will include the following elements:

- Participant (mother's) coded study identifier;
- Date of participant's last menstrual period;
- Total accumulated dose of study treatment administered to date;
- Date of study medication administration.

The investigator will follow the subject until completion of the pregnancy and must assess the outcome in the shortest possible time but not more than 30 days within completion of the pregnancy.

Upon delivery, miscarriage or abortion, the Principal Investigator or designee must forward a follow-up Pregnancy Report with any relevant information on the present condition of the fetus to the [REDACTED], including:

- Mother's coded study identifier(s);
- Gestational age at delivery, miscarriage or abortion;
- Birth weight, gender, length and head circumference, if available;
- Apgar scores recorded after birth, if available;
- Any abnormalities.

If the outcome of the pregnancy **meets the criteria for immediate classification of an SAE** (e.g., spontaneous or therapeutic abortion [any congenital anomaly detected in an aborted fetus is to be documented], stillbirth, neonatal death, or congenital anomaly), the investigator will report the event by phone and by faxing a completed SAE report form to [REDACTED] within one working day of being notified of the pregnancy report.

If the trial is completed before the outcome of the pregnancy is known, [REDACTED] will assume the responsibility for following up on the pregnancy. [REDACTED] will contact the Investigator or Study coordinator on or around the potential expected date of delivery to follow-up on the outcome of pregnancy and will also check on the status of the infant 8 weeks post-delivery. Upon awareness of the pregnancy outcome and known status of the infant following 8 weeks of delivery, the investigator will complete the applicable pregnancy report forms and fax to [REDACTED] within 1 day of being notified.

7.5 Post Study Adverse Events

7.5.1 Non-serious Adverse Events

Adverse events that are identified at the last assessment visit (or the early termination visit) must be recorded on the AE case report form (CRF) with the status of the AE noted.

7.5.2 Serious Adverse Events

Serious adverse events that are identified on the last assessment visit (or the early termination visit) must be recorded on the AE case report form (CRF) page and reported to Perrigo according to the procedures outlined above. Subjects with unresolved previously reported serious adverse events, or any new serious adverse events identified on the last assessment visit, should be followed by the investigator until the events are resolved, or the subject is lost to follow-up. Resolution means the subject has returned to the baseline state of health, or the investigator does not expect any further improvement or worsening of the adverse event. The investigator should continue to report any significant follow-up information to Perrigo up to the point that the event has resolved. Any serious adverse event reported by the subject to the investigator that occurs after the last assessment, and are determined by the investigator to be reasonably associated with the use of the study drug, should be reported to Perrigo.

8. STATISTICAL ANALYSIS

The sections that follow highlight sample size determination and the planned analyses for this study. A statistical analysis plan (SAP) will be prepared separately from this protocol which gives descriptions of the statistical methods, models, hypotheses and subject populations to be analyzed. The SAP will be completed and approved before locking the database and unblinding the

study and will serve as a companion to the protocol and the *de facto* documentation of the proposed statistical evaluation. The SAP will be completed and finalized prior to breaking the blind.

8.1 Statistical Analysis Plan

8.1.1 Analysis Populations

The following populations are defined for the purpose of analyses:

- Intent-to-Treat (ITT) (safety population): Any subject that was randomized received and used study medication.
- Modified Intent-to-Treat (mITT): Any subject, who met the inclusion/exclusion criteria, was randomized, received and used the study medication, and returned for at least one post-baseline efficacy assessment.
- Per Protocol (PP): Any subject:
 - Who met inclusion/exclusion criteria,
 - Who was randomized and received and used study medication,
 - Who met the protocol criteria for compliance [REDACTED]
[REDACTED] and [REDACTED]
[REDACTED]
 - Who completed Visit 4/Week 12/Day 84 (End of Treatment/Early Termination Visit) within window OR was dropped from the study due to treatment failure after at least 4 weeks of treatment with a compliance rate of at least 75%.
 - Without significant protocol violations that could have interfered with the administration of the treatment or the precise evaluation of treatment efficacy.

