15.2 Appendix B: Instructions for the Subject.....	45
15.3 Appendix C: Face Diagram	48
16. REFERENCES.....	49

STUDY SYNOPSIS

Title:	A Multi-Center, Double-Blind, Randomized, Vehicle-Controlled, Parallel-Group Study to Compare Perrigo UK FINCO Clindamycin Phosphate and Benzoyl Peroxide Topical Gel 1.2%/3.75% to Valeant Pharmaceuticals North America, LLC Onexton™ Topical Gel (Clindamycin Phosphate and Benzoyl Peroxide Gel 1.2%/3.75%), and Both Active Treatments to a Vehicle Control in the Treatment of Acne Vulgaris
Study Period:	12 weeks (84 Days)
Study Medication:	
 1. Clindamycin Phosphate and Benzoyl Peroxide Topical Gel 1.2%/3.75%, [REDACTED]. 2. Onexton™ Topical Gel (Clindamycin Phosphate and Benzoyl Peroxide Gel 1.2%/3.75%), Valeant Pharmaceuticals North America, LLC 3. Vehicle of test product, [REDACTED]
Study Objectives:	To compare the safety and efficacy profiles of Perrigo UK FINCO Clindamycin Phosphate and Benzoyl Peroxide Topical Gel 1.2%/3.75% to Valeant Pharmaceuticals Onexton™ Topical Gel (Clindamycin Phosphate and Benzoyl Peroxide Gel 1.2%/3.75%) and to demonstrate the superior efficacy of the two active formulations over that of the vehicle in the treatment of Acne Vulgaris.
Study Design:	Subjects in this multi-center, double-blind, randomized, vehicle-controlled, parallel-group study will be admitted into the study only after written informed consent/assent (as applicable) has been obtained and after all inclusion/exclusion criteria have been met. Male and female subjects 12 years to 40 years of age, inclusive, with acne vulgaris IGA score [REDACTED] will be eligible for enrollment.
Study Population:	Approximately [REDACTED] healthy males and females, 12 to 40 years of age, inclusive, who meet the inclusion/exclusion criteria, will be enrolled to obtain approximately [REDACTED] modified-Intent-To-Treat (mITT) and [REDACTED] per-protocol (PP) subjects.
Dosing:	Subjects will be randomized [REDACTED] to either the test product, reference product or vehicle treatment group, respectively, and will apply [REDACTED] the study medication onto six areas of the face (chin, left cheek, right cheek, nose, left forehead and right forehead) as a thin layer and avoiding contact with the eyes, lips, mouth, broken areas of the skin and mucous membranes at approximately the same time once daily for 12 weeks.

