Study Visits:	
Clinical Evaluations will be performed at:
 
 1. Visit 1/Day 1 (Baseline) 2. Visit 2/Week 4/Day 28 (± 4 days)(Interim) 3. Visit 3/Week 8/Day 56 (± 4 days)(Interim) 4. Visit 4/Week 12/Day 84 (± 4 days)(End of treatment/End study) 
Safety will be assessed by monitoring adverse events at each visit and at the

Protocol No: PRG-NY-15-003

	Week 2/Day 15 (± 4 days) Telephone Contact.
Evaluations:	The number of facial inflammatory and non-inflammatory lesions as well as the Investigator's Global Assessment (IGA) will be recorded at baseline and all subsequent visits.
Endpoints:	
The two primary efficacy endpoints will be the:
 
1) Mean percent change from baseline to Week 12 (Day 84) in the inflammatory (papules and pustules) lesion count and2) Mean percent change from baseline to Week 12 (Day 84) in the non-inflammatory (open and closed comedones) lesion count. 
The secondary endpoint will be the proportion of subjects at Week 12 with a clinical response of "success", defined as an IGA score that is at least 2 grades less than the baseline assessment.

Safety:	The incidence of all adverse events reported during the study will be summarized by treatment group. Equivalence of the test and reference with regard to safety will be evaluated by comparing the nature, severity and frequency of their adverse event profiles. In addition, the test and reference treatments' frequency and distribution of application site reactions of erythema, dryness, scaling/peeling, burning/stinging, erosion, edema, pain and itching will be summarized and compared descriptively.

ABBREVIATIONS

AE	Adverse Event
ANOVA	Analysis of Variance
CMH	Cochran–Mantel–Haenszel test
CRF	Case Report Form
DCF	Data Correction Form
FDA	US Food and Drug Administration
GCP	Good Clinical Practices
ICH	International Conference on Harmonization
IGA	Investigator's Global Assessment
IRB	Institutional Review Board
ITT	Intent- to-treat (population)
IU	International Unit
IUD	Intra-Uterine Device
LOCF	Last Observation Carried Forward
MedDRA	Medical Dictionary for Regulatory Activities
miITT	Modified Intent-to-Treat (population)
NSAID	Non-Steroidal Anti-Inflammatory Drug
OTC	Over the counter
PI	Principal Investigator
PP	Per- protocol (population)
Rx	Prescription
SAE	Serious Adverse Event
SAP	Statistical Analysis Plan
SPF	Sun Protection Factor
Sub-I	Sub-Investigator
UPT	Urine Pregnancy Test

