5.16 Subject/Treatment Compliance

Subjects will apply the medication onto six areas of the face (chin, left cheek, right cheek, nose, left forehead and right forehead) at approximately the same time once daily for 12 weeks. On Day 1, subjects will apply their initial dose of study medication [REDACTED]

[REDACTED] On Week 2 Day 14/

(± 4 days), compliance will be assessed via telephone contact. The study coordinator, or designee, will review the Subject Instruction Sheet and Diary with the subject on the phone. The total number of study medication doses applied and/or missed will be determined based upon the first dose applied through and including the last dose applied. The first and last dates of treatment

[REDACTED]

should be recorded on the CRF. The total of applied and missed study medication applications should also be recorded. By definition there are no missed applications before the first date of treatment or after the last date of treatment.

[REDACTED]. All used and unused pump bottles of study medication will be collected by the study site at appropriate visits or early termination.

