5.17 Discontinuation/Withdrawal of Study Subjects

Subjects may be removed from the study for any of the following reasons:

- The subject withdraws his or her consent for any reason.
- The subject's condition has worsened to the degree that the investigator feels it is unsafe for the subject to continue in the study.
- The subject's medication code is unblinded.
- Subject did not meet or no longer meets the entry criteria.
- An adverse event including intercurrent illness, occurs for which the subject desires to discontinue treatment or the investigator determines that it is in the subject's best interest to be discontinued.
- The subject is lost to follow-up. The investigator will document efforts to attempt to reach the subject twice by telephone and will send a certified follow-up letter before considering that subject lost to follow-up. All attempts must be thoroughly recorded.
- The subject becomes pregnant during the course of the trial.
- Lack of efficacy (treatment failure) after 4 weeks (30 days) of compliant treatment (investigator removal from study).
- Investigator discretion

After a subject has been discontinued, he/she will not be allowed to re-enroll in the study.

The reasons for a subject being discontinued will be documented in the case report (CRF) form and the enrollment log.

If a subject is discontinued from the study for any reason, the Visit 4 (Day 84)/ End of Study Visit/Early Termination Visit procedures should be completed and any outstanding data and study medication should be collected. Data, in addition to the reason for discontinuation and the date of removal, will be recorded on the Source Document and End of Study Case Report Form.

In the event that a subject discontinues from the study at any time due to an adverse event, the reason for discontinuation, the nature of the event and its clinical course must be fully documented. For such a subject, the investigator must strive to follow the subject until the adverse event has resolved, become clinically insignificant, is stabilized, or the subject is lost to follow-up.

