5.6 Safety Variables and Analyses

Duration of Treatment and Medication Compliance

Number of applications, days of exposure, and compliance rate will be summarized by treatment group using descriptive statistics. For each subject, the overall duration of treatment (days) will be calculated using the following formula:

$$\text{(Date of last application of study medication)} - \text{(Date of first application of study medication)} + 1.$$

Medication compliance rate (%) will be calculated for each subject as follows:

$$\text{(Total number of applications used)} / \text{(Expected number of applications)} *100\%.$$

Adverse Events

Adverse events (AEs) will be coded in MedDRA, version 15.1. Treatment-Emergent Adverse Event (TEAE) is defined as any AE occurs on or after applying the first dose of study drug. Number and percent of subjects reporting TEAEs will be tabulated by treatment group. Summaries will be presented by body system and preferred term for the ITT population. Similar tables will be presented by severity and relationship to study drug. TEAEs reported by more than 5% subjects for any treatment group will also be summarized. In summaries of incidence rates (frequencies and percentages), severity and relationship to study drug, subjects who report more than one event that are mapped to the same preferred term will be counted only once under the strongest severity and relationship, accordingly. The difference between Test and Reference treatments with regard to the severity and frequency of their dermatological adverse events will be statistically evaluated. Fisher's exact test will be used to compare the proportions of subjects of the two active treatment groups who report any TEAE.

Treatment-Emergent Serious Adverse Events (TESAEs) and TEAEs that led to treatment interruption or discontinuation will be presented in [data listings](#).

Concomitant Medications

Concomitant medications will be coded using the WHO Drug Dictionary, version September, 2014, and will be presented in [data listings](#).

Application Site Reactions

Frequency and distribution of application site reactions of erythema, dryness, scaling/peeling, burning/stinging, erosion, edema, pain and itching will be summarized and compared descriptively by visit.

Safety comparisons will be performed only for the ITT population.

6 Appendices

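### Does the undefined denominator in SAP 5.6 shut early treatment failures out of the per-protocol population?

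*Protocol*

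**What the plan says.** Protocol 8.1.1 gives two routes into the PP population. The first is to complete the Week 12 visit on time. The second is for a subject who "was dropped from the study due to treatment failure after at least 4 weeks of treatment with a compliance rate of at least 75"%. PP is the definitive population for equivalence (Protocol 8.1.4, SAP 5.5.1).

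The only visible formula for compliance is in SAP 5.6. It opens "Medication compliance rate (%) will be calculated for each subject as follows" and divides the applications used by "Expected number of applications", with no definition of that term. The section covers safety variables, and its compliance table (Table 14.3.1) is for the intent-to-treat population.

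Protocol 5.16 says how doses are counted: applied and missed doses are "determined based upon the first dose applied through and including the last dose applied", and "By definition there are no missed applications before the first date of treatment or after the last date of treatment". It states no rate in its visible text.

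The synopsis gives the study period as "12 weeks (84 Days"), with one application a day. Protocol 5.17 lists as a ground for removal: "Lack of efficacy (treatment failure) after 4 weeks (30 days) of compliant treatment (investigator removal from study").

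**The concern.** A rate with an undefined denominator can be computed in more than one way, and here the choice seems to decide who is analysed. If an analyst set the denominator to 84 for everyone, each subject removed for lack of efficacy at an in-window Visit 2 or Visit 3 would miss the 75% limit, however well they had dosed. The treatment-failure route into PP would then be closed for most of the trial.

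That matters because PP decides equivalence. Dropping failures removes poor responses. If Test had more of them than Reference, dropping them would move a Test-to-Reference ratio that is below 1 closer to 1, which favours a finding of equivalence. If both arms had the same share, and those failures averaged no change, the ratio would not move.

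**Working it through.** The plan states no figure to reproduce, so the check is arithmetic on its rules.

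**Inputs.** Limit of 75% after at least 4 weeks (Protocol 8.1.1). One application a day from Day 1 for 84 days (synopsis, Protocol 5.16), and no more than one a day (Protocol 4.4). Visit 2 on Day 28 ± 4, and Visit 3 given as "Visit 3/Week 8/Day 56 (± 4 days)(Interim"), so Days 52 to 60.

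**Reading A, 84 expected.** Doses needed: 0.75 × 84 = 63, so Day 63 at the earliest. With 80 or 88 expected, to allow for the Visit 4 window, the need is 60 or 66 doses.

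**Reading B, the Protocol 5.16 count.** The denominator is the days from first to last dose.

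| Last dose, none missed | Reading A | Reading B | Doses needed for 75% under B |
|---|---|---|---|
| Day 28 | 28/84 = 33.3% | 28/28 = 100% | 21 |
| Day 30 | 30/84 = 35.7% | 100% | 23 |
| Day 52 | 52/84 = 61.9% | 100% | 39 |
| Day 56 | 56/84 = 66.7% | 100% | 42 |
| Day 60 | 60/84 = 71.4% | 100% | 45 |
| Day 63 | 63/84 = 75.0% | 100% | 48 |

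Reading B still tests something: at Day 28 it fails anyone with more than 28 − 21 = 7 missed doses, and at Day 56 more than 56 − 42 = 14.

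**Which reading fits the text.** In Protocol 8.1.1 the rate qualifies the treatment received over at least 4 weeks. Protocol 5.17 speaks in the same way of compliant treatment over that period. Under A, perfect dosing for 4 weeks scores 33.3%, so the 4-week entry point could never operate at 4 weeks. A reading that disables the clause it is meant to apply is unlikely to be the intended one.

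**A third option, doses scheduled from first dose to removal.** For a subject who dosed daily until removal this also gives 100%, so it agrees with B. The two differ only for someone who stopped applying well before removal. With no missed dose up to last-dose day L and removal on day R, the rate is L/R. The 4-week condition gives L of at least 28. Since 28/37 = 75.7% and 28/38 = 73.7%, they cannot disagree for removals up to Day 37. At R = 56 they disagree only if L is below 0.75 × 56 = 42.

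**Possible effect under A.** If failures average no change and are left out, the ratio becomes the true ratio × (1 − fR)/(1 − fT), where fR and fT are the failure shares. At a true ratio of 0.80, shares of 1% (Reference) and 2% (Test) give 0.80 × 0.99/0.98 = 0.808. Shares of 2% and 4% give 0.80 × 0.98/0.96 = 0.817. Simulated on one endpoint with 200 or 400 per arm (Reference non-failure mean 60%, SD 35), the chance of wrongly passing rises from 5.0% to 6.8% or 7.6% in the first case, and to 9.1% or 11.4% in the second. The shares, means, SD, arm sizes and true ratio are all assumed. If both lesion counts must pass, these are upper bounds for the trial as a whole.

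**The case for a change.** The strongest case for a change is that SAP 5.6 states one formula for every subject and does not separate completers from those removed early. Coding 84 throughout would contradict nothing in that section. Protocol 5.16 does not use the SAP's term, and its count does not suit every subject: a completer who stopped dosing on Day 42 scores 42/42 = 100%, against 42/84 = 50% on the full course. Protocol section 8 makes the SAP the place where populations are described, and a sentence there would cost little.

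Part of this stands. The term is undefined in the visible text, and the two sensible counts can differ for a failure who stopped applying long before removal. Protocol 5.16 does address that case, since days after the last dose are not counted as missed. The completer example shows no error, because the compliance limits for completers are redacted and its effect on PP cannot be judged.

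The step from SAP 5.6 to PP membership is also an inference. The compliance criterion in both PP definitions, the text after the missed-dose rule in Protocol 5.16, the SAP's own copy of the treatment-failure clause and the whole of SAP 5.2 are redacted. Any of these may define the rate, and text hidden by redaction cannot be counted as missing from the plan.

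**Conclusion.** No change follows. This is a detail left to the analyst, and the surrounding text leads to a sensible choice. The Day 63 threshold is correct arithmetic for an 84-dose denominator, but that denominator defeats the 4-week clause. Both workable counts, first to last dose or first dose to removal, give 100% to a fully dosed treatment failure on any removal day, so none is lost from PP on this ground. Removals on Days 24 to 27 of the Visit 2 window fail the 4-week condition whatever the denominator.

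The shift in the ratio arises only under the implausible reading, and then only if Test has more failures than Reference. The documents give no failure rate, so its size is unknown.

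The conclusion assumes one dose a day from Day 1 and that no redacted text imposes a full-course denominator on treatment failures.
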